## 5.2. Baseline Definitions

For safety parameters the baseline or pre-dose value will be the latest assessment prior to the time of study drug administration in each phase with a non-missing value, including those from unscheduled visits. If time is not collected, Day 1 assessments are assumed to be taken prior to first dose and considered for use as baseline. If there are multiple assessments collected on the same scheduled time, the average of these assessments will be used. [Table 6](#) indicates the baseline day to be used in the analysis.

**Table 6 Baseline Parameter Specifications**

Phase	Parameter	Study Assessments Considered as Baseline	Baseline Used in Data Display
Oral Lead-in Phase	Laboratory results, Vital Sign results, ECG results 	OLI Baseline = last non-missing pre-dose assessment collected <= Date of first OLI dose	OLI Day 1
Injection Phase	Laboratory results, Vital Sign results (pre-dose), ECG results  (pre-dose), CCI scores	Injection Phase Baseline = assessment collected on the date of CAB + RPV injection	Injection Day 1
Follow-up Phase	Laboratory results, Vital Sign results (pre-dose), ECG results  (pre-dose)	Follow-up Phase Baseline = assessment collected on the date of CAB + RPV injection	Injection Day 1

1. Average of the triplicate assessments for quantitative assessments will be used as the baseline.

If time is not collected, Day 1 assessments are assumed to be taken prior to first dose of the respective phase. Unless otherwise stated, if baseline data is missing no derivation will be performed and baseline will be set to missing.

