### 2.3.1. Risk Assessment

Potential Risk of Clinical Significance	Summary of Data/Rationale for Risk	Mitigation Strategy
Drug Induced Liver Injury (DILI)	
A small proportion of participants in the CAB program to date (total exposure >3100 participants) have developed transaminitis (elevated liver transaminases characterized by predominant alanine aminotransferase (ALT) elevation). In most participants, transient transaminitis was explained by acute viral hepatitis infection (. In a small number of participants, there was not an alternative explanation, suggesting a mild form of drug induced liver injury (DILI) without hepatic dysfunction, which resolved upon withdrawal of treatment with CAB.
 
All participants with suspected DILI identified to date were receiving oral CAB.
	
 
Exclusion criteria as described in Section 5.2 will prohibit participation with significant liver impairment based on screening liver chemistry including transaminases (ALT and Aspartate aminotransferase [AST]) as well on prior medical history.
 
A 4-week oral lead-in Phase is being implemented in this study, where all participants will receive oral CAB prior to the administration of IM CAB to assess individual safety and tolerability. Liver transaminases (ALT and AST) will be monitored throughout this study (refer to Schedule of Activities) and the liver chemistry stopping criteria will be adopted as described in Section 7.1.1 of this protocol.
 
All instances of liver transaminase elevations of Grade 2 and above will be followed to resolution. Participants withdrawn from the study due to meeting liver chemistry stopping criteria will be regularly monitored both clinically and using liver chemistries to determine progress towards resolution of the liver event.
 

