## **7.6. Clinical Laboratory Evaluations**

Worst grade post-baseline for hematology, clinical chemistry, and urinalysis data will be summarized by study phase. Summaries of change from baseline in hematology and clinical chemistry by study phase and visit will be created. If any laboratory test results are outside of the reference range, they will be flagged with high/low and/or toxicity grade in the listing. Standardized units will be used for clinical laboratory summary tables and listings.

Hematology, clinical chemistry, drug, infectious disease, coagulation and urinalysis data will be listed by subject, study phase, visit, and collection date.

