**Table 3 Assignment of Study Phases**

For All Events or Assessments	
Study Period	Date range
Screen	If actual “Time of Day” for the assessment/event is collected: Start Date and Time < OLI Treatment Start Date & Time
	If actual “Time of Day” for the assessment/event is not collected:
	Start Date < OLI Treatment Start Date
OLI Phase	If actual “Time of Day” for the assessment/event is collected: For participants continuing into Injection Phase: OLI Treatment Start Date & Time ≤ Start Date & Time < Date & Time of CAB + RPV Injection
	For participants not continuing into Injection Phase: OLI Treatment Start Date & Time ≤ Start Date & Time
	If actual “Time of Day” for the assessment/event is not collected:
	For participants continuing into Injection Phase: OLI Treatment Start Date ≤ Start Date < Date of CAB + RPV Injection
	For participants not continuing into Injection Phase: OLI Treatment Start Date ≤ Start Date
Injection Phase	If actual “Time of Day” for the assessment/event is collected: Date & Time of CAB + RPV Injection ≤ Start Date & Time and Start Date ≤ Date of Nominal Follow-up Week 4
	If actual “Time of Day” for the assessment/event is not collected:
	Date of CAB + RPV Injection ≤ Start Date ≤ Date of Nominal Follow-up Week 4 Visit
Follow-up Phase	Date of Nominal Follow-up Week 4 Visit < Start Date

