**CONFIDENTIAL**

208832

Laboratory: Urinalysis					
3.31.	Safety	UR1	Summary of Worst-Case Urinalysis Results (Discrete or Character Values) Post-Baseline Relative to Baseline by Study Phase	ICH E3 Note: Define change categories according to actual values expected from lab dataset Repeat for each study phase and overall	SAC
Laboratory: Hepatobiliary (Liver)					
3.32.	Safety	LIVER1	Summary of Liver Monitoring/Stopping Event Reporting by Study Phase and Overall	GSK Statistical Display Standard Note: See Appendix 11.4.4 for Criteria	SAC
3.33.	Safety	LIVER10	Summary of Hepatobiliary Laboratory Abnormalities by Study Phase and Overall	GSK Statistical Display Standard Note: See Appendix 11.4.4 for Criteria	SAC
ECG					
3.34.	Safety	EG2	Summary of Change from Baseline in ECG Values by Study Phase and Visit	GSK Statistical Display Standard	SAC
3.35.	Safety	EG2	Summary of ECG Values by Study Phase and Visit	GSK Statistical Display Standard	SAC
3.36.	Safety	EG1	Summary of ECG Findings by Study Phase and Visit	GSK Statistical Display Standard	SAC
Vital Signs					
3.37.	Safety	VS1	Summary of Change from Baseline in Vital Signs by Study Phase and Visit	ICH E3	SAC

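### An untimed injection-day laboratory record is taken as pre-injection for baseline but assigned to the Injection Phase, so an abnormality first seen on it misses both phases' worst-grade tables

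*SAP*

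**What the plan says.** **Baseline.** SAP 5.2 gives the rule for records without a clock time: "If time is not collected, Day 1 assessments are assumed to be taken prior to first dose and considered for use as baseline". The note under Table 6 repeats it phase by phase: "If time is not collected, Day 1 assessments are assumed to be taken prior to first dose of the respective phase". For laboratory results, Table 6 sets "Injection Phase Baseline = assessment collected on the date of CAB + RPV injection".

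**Phase.** SAP Appendix 3 (11.3.1, the table on assignment of study phases) covers all events and assessments and has two branches. With a clock time, a record belongs to OLI up to the moment of injection. The other branch applies when the time of day "for the assessment/event is not collected". There, for participants who go on to injection, OLI requires "OLI Treatment Start Date ≤ Start Date < Date of CAB + RPV Injection", and the Injection Phase starts on the injection date itself.

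**Displays.** SAP 7.6 says: "Worst grade post-baseline for hematology, clinical chemistry, and urinalysis data will be summarized by study phase". Tables 3.27 (chemistry) and 3.30 (hematology) carry this out as post-baseline grade increases, repeated for each phase, with no overall column mentioned. The liver displays are by phase plus overall: Table 3.32 for monitoring and stopping events, and Table 3.33, titled "Summary of Hepatobiliary Laboratory Abnormalities by Study Phase and Overall". The criteria in SAP 11.4.4 state no post-baseline restriction.

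**Context.** SAP 5.1 counts washout safety events with OLI. On drug-induced liver injury (DILI), Protocol 2.3.1 says: "All participants with suspected DILI identified to date were receiving oral CAB".

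**The concern.** The two SAP rules place the same untimed record on opposite sides of the injection. For baseline it is before; for phase it is in the Injection Phase. A pre-dose draw with a time recorded goes to OLI. The phase that an abnormality is credited to would then depend on whether a clock field exists and was filled in.

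The injection-day draw matters because the schedule shows no assessments in the 10 to 14 day washout, which Protocol Appendix 8 allows to be extended for COVID-19. Injection-day chemistry, if drawn before the injection, is the first scheduled look after Day 29 and the last look at the effects of oral dosing. Liver safety is a stated secondary objective in SAP 2.2. A late rise after oral dosing could be missing from the worst-grade tables, or could appear in a liver table under the injection.

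**Working it through.** No sample-size or power figure bears on this. The check is a trace of the SAP's own rules for one raised laboratory value drawn before the injection, on the injection day.

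**Inputs.** OLI dosing runs 28 days and washout 10 to 14 days (Protocol 4.1), so the injection falls on about OLI Phase Day 28 + 10 = 38 to 28 + 14 = 42. For illustration only, assume the draw is at 08:00 and the injection at 10:00. About 15 participants are injected (Protocol 10.2).

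**Trace.** The result is the same for both washout lengths.

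| Step | Time recorded | No time recorded |
|---|---|---|
| OLI condition (Appendix 3) | 08:00 is before 10:00: met | date is not before the injection date: not met |
| Phase assigned | OLI | Injection |
| Used as Injection baseline (5.2, Table 6) | yes | yes, by assumption |
| In OLI post-baseline worst grade | yes | no, wrong phase |
| In Injection post-baseline worst grade | no | no, it is the baseline |
| In Injection if a display counts every record in the phase | no | yes |

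The untimed value therefore enters neither column of Tables 3.27 and 3.30. The last row bears on Tables 3.32 and 3.33, and applies only if their shells keep baseline records.

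**Same rule at OLI Day 1.** An untimed record on that day is also both OLI and baseline. Nothing is lost there, because no study drug precedes it and Screening has no worst-grade column. On the injection day, four weeks of oral dosing precede the draw.

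**Size.** One participant in the injected group is 1/15 = 6.7 percentage points. If the number injected were between 12 and 18 (an assumed range), it would be 1/12 = 8.3 to 1/18 = 5.6 points. The oral column has everyone dosed orally as its denominator, so the shift there is slightly smaller if more than 15 started oral dosing.

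**Visit slotting.** SAP Appendix 2 assigns phase before visit. For laboratory data, Table 8 places every OLI record from OLI Phase Day 22 onward in the Day 29 window. An injection-day record labelled OLI would sit 38 − 29 = 9 to 42 − 29 = 13 days from that target. SAP 11.5.1 uses the value closest to target, so a true Day 29 record would win. If that visit was missed, the injection-day value would be reported as Day 29. The Injection Day 1 row of Table 9 would also lose its pre-dose record. A timed pre-dose record already meets this problem.

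**The case against.** The strongest reply is that a baseline flag and a phase label are separate variables. The untimed rule agrees with Table 6, which names the display baseline Injection Day 1, and with Table 9, which slots Phase Day 1 laboratory records under Injection. On that view the timed rule is the odd one out. This stands for the visit label, and the fix must respect it. It does not answer the worst-grade tables, where the two labels together remove the value from both phases. Nor does it fit SAP 5.1 on washout, or the note to the concomitant-medication table in Appendix 3, which does carry a pre-dose assumption into phase assignment.

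Several stronger readings are tempting, and the documents do not support them:

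- *The value disappears.* It stays in the laboratory listing (Listing 17), in the Injection Day 1 by-visit summaries and, if criteria are met, in Listings 32 and 33. Tables 3.32 and 3.33 also have an overall display. ALT at or above 3 times the upper limit of normal has its own reporting route in Protocol Appendix 6.
- *It is charged to the injection.* Tables 3.32 and 3.33 follow standard shells (LIVER1, LIVER10) that are not shown. Whether they drop baseline records is unknown, so this is only possible.
- *Injection-day chemistry is a stated pre-dose draw.* Table 6 adds a pre-dose label to vital signs and ECG but not to laboratory results, and the injection-day checks in the schedule's footnote 2 do not include chemistry. The pre-dose status of an untimed laboratory record comes from the 5.2 assumption alone.
- *Many records are affected.* SAP 7.6 lists laboratory data by collection date, while SAP 7.7 lists vital signs with actual date and time. That makes laboratory records the likelier case, but the documents do not say that their times are missing.
- *A phase comparison is compromised.* SAP 2.4.1 plans no formal comparison, and safety is descriptive.

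**Conclusion.** The inconsistency is real and nothing in the documents reconciles it. For laboratory records dated on the injection day with no clock time, an abnormality first seen there is absent from both phases' post-baseline worst-grade tables. It may be counted under Injection in the by-phase liver tables, depending on shells that cannot be seen.

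The point is minor. It affects summary tables, not the retention of data. Its size is 6.7 points per affected participant with 15 injected, and the number affected cannot be worked out. The conclusion assumes that the 5.2 rule and the Appendix 3 rule are both programmed literally, and that at least one injection-day laboratory record with a new abnormality has no time. If every such draw is timed, the worst-grade and liver displays are unaffected. It does not extend to AEs, for which assigning an untimed injection-day event to the Injection Phase can stand, or to vital signs and ECG, whose planned tables are by visit.

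**What to change.** Add to SAP 11.3.1, in substance:

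- An untimed laboratory record dated on the injection day and used as Injection baseline under Section 5.2 is counted with OLI/washout in the worst-grade and hepatobiliary displays (Tables 3.27, 3.30, 3.32, 3.33), as a timed pre-dose record already is by phase. It is not counted as an Injection Phase event, and it remains the Injection and Follow-up baseline.
- For visit slotting, all pre-dose injection-day laboratory records, timed or untimed, stay at Injection Day 1 (Table 9) and are excluded from the Day 29 window of Table 8.

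The rule should key on use as Injection baseline rather than on being scheduled pre-dose, because the documents do not label the chemistry draw that way. Leave the AE rule and the by-visit vital-sign and ECG tables unchanged.

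The cost is one or two sentences and a small programming change, with no new data collection. SAP 11.9 describes the display list as tentative, so the change is easy to make now. After database freeze it would become a choice about individual values already seen.

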## 5.3. Other Considerations for Data Analyses and Data Handling Conventions

### 5.3.1. Other Considerations

Other considerations for data analyses, including information regarding premature withdrawal, unscheduled assessments, derived and transformed data, and data handling conventions are outlined in the appendices:

Section	Component
11.1	Appendix 1: Schedule of Activities
11.2	Appendix 2: Assessment Windows
11.3	Appendix 3: Study Phases and Treatment Emergent Adverse Events
11.4	Appendix 4: Data Display Standards and Handling Conventions
11.5	Appendix 5: Derived and Transformed Data
11.6	Appendix 6: Reporting Standards for Missing Data

Section	Component
11.7	Appendix 7 : Values of Potential Clinical Importance
11.8	Appendix 8 : Abbreviations & Trademarks
11.9	Appendix 9 : List of Data Displays
11.10	Appendix 10 : AESI Identification

## 6. STUDY POPULATION

The study population analyses will be based on both the Enrolled and Safety populations, unless otherwise specified.

Study population analyses include analyses of study populations, subjects' disposition, important protocol deviations, demographic and baseline characteristics, and prior and concomitant medications. Outputs will be based on GSK Core Data Standards. Details of the planned displays are presented in Appendix 9: List of Data Displays.

### 6.1. Subject Disposition

A summary table will be generated to provide the count of subjects included in each analysis population for the study (see Section 4 for definition of analysis populations).

The End of Study Record will be summarized by study phase and overall. Counts for the all discontinuation categories will be repeated considering subjects who discontinued to a Covid-19 related incident.

A disposition listing will include whether subjects prematurely withdrew from the study, the reason for premature discontinuation along with the start and end date of investigational product (IP) dosing and the date of completion or premature discontinuation from the study. An additional listing showing subjects who discontinued to Covid-19 considerations will be included.

### 6.2. Demographic and Baseline Characteristics

Demographic data include date of birth, sex, race, and ethnicity. Demographic data and baseline characteristics (i.e. height, weight, and BMI) will be summarized for the Safety Population. Race will be further summarized separately from the other demographic characteristics. All demographic data will be listed by subject.

### 6.3. Medical History and Concomitant Medications

Medical history events will be summarized and listed. Concurrent medication verbatim text will be coded and classified by the Anatomical Therapeutic Chemical Classification level 1 (ATC Level 1) code and the preferred term using the GSK coding system, GSK DRUG. Concomitant medications will then be summarized by ATC classification, study phase, and overall. Coding of concurrent medications will be the responsibility of the GSK coding group.

## 7. SAFETY ANALYSES

Safety data will be summarised and listed by, or under the direct auspices of, Clinical Statistics, GlaxoSmithKline. The safety summaries will be based on the Safety population, unless otherwise specified and shown for the Oral Lead-in, Injection, and Follow-up phases where applicable.

Safety endpoints include:

- Safety and tolerability parameters including adverse events, clinical laboratory tests, ECG, and vital sign assessments
- Tolerability parameters (liver related adverse events) and liver chemistry abnormalities

For continuous safety parameters, the Injection phase Baseline will also serve as Follow-up phase Baseline. No formal statistical analysis of the safety data will be conducted. The precise format and content of Safety tables and listings are shown in [Appendix 9](#) of the RAP.

## **7.1. Extent of Exposure and Treatment Compliance**

Overall CAB & RPV exposure will be presented with descriptive statistics (i.e. n, mean, SD, median, minimum, and maximum) by study phase and treatment. Treatment will be determined by the laterality of the injection. CAB will be administered on a subject's *left* thigh while RPV will be administered on a subject's *right* thigh. Parameters displayed will include number of days of oral exposure, oral compliance percentage, and injection status. Details on oral compliance percentage calculation are included in [Appendix 5](#).

A by-subject listing of data on subject exposure will be generated including dose date and time, unit, formulation, route, frequency and location.

## **7.2. Adverse Events**

Adverse event verbatim text will be coded and classified by system organ class (body system) and preferred term using a standardized GSK coding system: Medical Dictionary for Regulatory Activities (MedDRA, v23.0 or higher). AE data will be summarized with frequencies and percent by study phase and overall. The relationship of AE system organ class, preferred term, and verbatim text will be listed. Treatment emergent AEs, drug-related AEs, serious adverse events (SAEs) including fatal AEs, and AEs leading to drug withdrawal or study discontinuation will be summarized by study phase and overall. AEs and drug-related AEs will also be summarized by maximum toxicity grade (based on Division of AIDS (DAIDS) categories). All AEs will be listed by subject and AE start date.

Adverse events related to Covid-19 will also be summarized by SOC, PT, and maximum toxicity. Subjects with Covid-19 tests performed as well as Covid-19 diagnoses will also be summarized. Summaries of serious Covid-19 AEs and Covid-19 AEs leading to study discontinuation or drug withdrawal will also be presented in accordance with Covid-19 safety assessment guidance. Covid-19 AEs will also be presented by sex and pandemic course (during and post-) if applicable.

## **7.3. Injection Site Reaction Adverse Events**

Injection site reaction adverse event data will also be summarized by treatment and overall. Tables will include subject and event-level summaries. ISR treatment will be determined by the laterality of the assessment (left vs. right). All ISR AEs will be shown in a separate listing from overall adverse events.

## **7.4. Adverse Events of Special Interest (AESIs)**

AESIs will be summarized for Hepatotoxicity and Seizures. QT Prolongation events will be listed. A comprehensive list of MedDRA terms based on clinical review will be used to identify each type of event for Adverse Events of Special Interest (AESI). [Changes to the MedDRA dictionary may occur between the start of the study and the time of reporting and/or emerging data from on-going studies may highlight additional adverse events of special interest, therefore the list of terms to be used for each event of interest and the specific events of interest will be based on the safety review team (SRT) agreements in place at the time of reporting.] The details of the current planned grouping, including Standardized MedDRA Query (SMQ) values (as applicable), and planned displays are provided in [Appendix 10: AESI Identification](#) and [Appendix 9: List of Data Displays](#).

## **7.5. Pregnancies (as applicable)**

If any female subjects become pregnant during the study, a listing of such subjects will be provided.

## **7.6. Clinical Laboratory Evaluations**

Worst grade post-baseline for hematology, clinical chemistry, and urinalysis data will be summarized by study phase. Summaries of change from baseline in hematology and clinical chemistry by study phase and visit will be created. If any laboratory test results are outside of the reference range, they will be flagged with high/low and/or toxicity grade in the listing. Standardized units will be used for clinical laboratory summary tables and listings.

Hematology, clinical chemistry, drug, infectious disease, coagulation and urinalysis data will be listed by subject, study phase, visit, and collection date.

## **7.7. Other Safety Analyses**

Vital sign data (temperature, systolic and diastolic blood pressure, and pulse rate) will be summarized by study phase, visit, and planned time. Absolute values and change from baseline values will be shown. Injection phase Baseline will also serve as Follow-up phase Baseline. Vitals signs will be listed by subject, study phase, visit, planned time, and actual date and time.

Electrocardiogram (ECG) data including values and findings will be summarized by study phase, visit, and timepoint. Absolute values and change from baseline will be shown for PR, QRS, QT, QTcB, and QTcF results. Baseline will be calculated as the mean of triplicate readings recorded prior to first dose in each study phase.

All ECG data including clinical interpretation will be listed by subject, study phase, visit and record date. Clinically significant ECG abnormalities will be flagged and listed separately, and corresponding values will be provided.

Liver related adverse events and chemistry abnormalities will be summarized separately by study phase. See [Appendix 10](#) for a list of Hepatotoxicity AEs and [Appendix 7](#) for Chemistry values of Potential Clinical Importance.

